If no DLTs are observed, then dose levels in Part I and Part II will be assessed for the fraction of patients with immunogenicity and clinical outcomes to determine the biologically optimal vaccine dose that would be used in any future phase II studies involving those respective patient populations.

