### 3.4 STUDY CALENDAR

Study Procedures	Screen	Wk 0	Wk 4	Wk 8	Wk 12	Wk 16	Wk 20	Wk 24	Wk 28	Wk 32	Wk 36	Wk 40	Wk 48 	Wk 60 	Wk 76 	Wk 100 	Wk 124 
NIH Advanced Directives 	✓																
Informed Consent	✓																
Height/Wt/NYHA	✓																
Screening labs/HLA 	✓																
Physical Exam/ECOG 	✓	✓	✓	✓	✓	✓	✓	✓	✓	✓	✓	✓	✓	✓	✓	✓	✓
Concomitant Medications	✓	✓	✓	✓	✓	✓	✓	✓	✓	✓	✓	✓	✓	✓	✓	✓	✓
Clinical labs 	✓	✓	✓	✓	✓	✓	✓	✓	✓	✓	✓	✓	✓	✓	✓	✓	✓
Tumor Markers 	✓	✓	✓	✓	✓	✓	✓	✓	✓	✓	✓	✓	✓	✓	✓	✓	✓
LDH/CK/Troponin 	✓	✓	✓	✓	✓	✓	✓	✓	✓	✓	✓	✓					
TSH/25-OH Vit D	✓	✓							✓					✓			
Lymphocyte Subsets/ Ig QA/IgE	✓	✓	✓	✓	✓	✓	✓	✓	✓	✓	✓	✓	✓	✓	✓	✓	✓
Serum beta HCG 	✓	✓	✓	✓	✓	✓	✓	✓	✓	✓	✓	✓					
Urinalysis	✓	✓							✓					✓			
Anti-HER2 Ab/ Profile 		✓		✓		✓		✓		✓		✓	✓	✓	✓	✓	✓
Anti-Ad5 Antibody 		✓		✓		✓		✓		✓		✓	✓	✓	✓	✓	✓
Cellular HER2 Response 		✓		✓		✓		✓		✓		✓	✓	✓	✓	✓	✓
Immune Subset/CTCs 		✓		✓		✓		✓		✓		✓	✓	✓	✓	✓	✓
Hitachi mRNA		✓															
MRI Brain  , CT Neck  , bone scan 	✓			✓		✓		✓		✓		✓	✓	✓	✓	✓	✓
CT Chest/Abd/Pelvis 	✓			✓		✓		✓		✓		✓	✓	✓	✓	✓	✓
2-D ECHO 	✓		✓		✓		✓		✓		✓	✓	✓	✓	✓	✓	✓
AdHER2 DC vaccine 	Apheresis	✓	✓	✓		✓		✓		✓							
Vaccine Report Card		✓	✓	✓		✓		✓		✓							
Adverse Events		✓	✓	✓	✓	✓	✓	✓	✓	✓							

 As indicated in Section 12.3, all subjects  $\geq$  age 18 will be offered the opportunity to complete an NIH advanced directives form. This should be done preferably at baseline but can be done at any time during the study as long as the capacity to do so is retained. The completion of the form is strongly recommended, but is not required

 Screening labs: CBC diff, PT/PTT, acute care panel, hepatic panel, serum beta HCG, urinalysis, and the following DTM labs: Anti-HIV 1/2 Ab, Anti-HCV Ab, HBsAg, Anti-HBs Ab, anti-HTLV 1/2 Ab (pending result is acceptable for eligibility), anti-CMV IgG/IgM, and RPR. If DTM labs are performed  $>$  30 days prior to apheresis, DTM labs must be repeated. HLA will not determine eligibility and if it was done previously at the NIH it does not need to be repeated.

 Patients should be evaluated within 7 days prior to upcoming vaccination as a clearance for treatment.

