 Dose can be delayed up to 8 weeks. The study will reset at the time of study resumption. For example, if dose at week 8 is delayed and resumed at original week 11, that week 11 will now be considered week 8.

 If there is a need for confirmatory scans based on the result of Week 48 evaluation, additional visit will occur at week 52 which will include clinical assessment with physical exam and laboratory assessment.

 Patients who progress do not require a full evaluation. Only physical exam, clinical labs, echocardiogram and AE reports will be required.

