### **11.1 PART I (MAXIMUM OF 30 EVALUABLE PATIENTS)**

The goal of Part I is to investigate vaccine dose escalation and determine whether there is a significant, adverse safety signal regarding cardiac toxicity in patients with recurrent or progressive, metastatic solid tumors as well as adjuvant bladder cancer patients with HER2 expressing tumors that are naive to trastuzumab, lapatinib, ado-trastuzumab and other HER2-directed therapies, in addition to preliminary assessment of the vaccine's immunogenicity and clinical activity. Allowable tumors include breast, ovarian, colon, non-small cell lung, renal cell, bladder and prostate cancer with HER2 characterization by IHC and FISH as outlined in Section **2.1.1.14**.

Inclusion of a broad spectrum of tumors that express HER2 will facilitate more rapid accrual and allow prompt determination of the vaccine's safety and immunogenicity. However, the inclusion

of subjects with multiple tumor types that have varying levels of HER2 expression may preclude identification of an optimal biologically active dose.

During this part, vaccine safety, immunogenicity and preliminary activity will be determined for each dose level given escalating doses of vaccine as follows:

Dose Level 1 (N = 6 patients):	$5 \times 10^6$ viable cells/vaccine
Dose Level 2 (N = 6 patients):	$10 \times 10^6$ viable cells/vaccine
Dose Level 3 (N = 6 patients):	$20 \times 10^6$ viable cells/vaccine
Expansion Cohort (N= 12 patients):	$40 \times 10^6$ viable cells/vaccine

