Since 0 of 20 patients already have been documented to have NO cardiac toxicity, and 0 to 2 patients out of 30 would have been acceptable per the original study design, a statistical estimate was performed to determine what the probability of having 0 to 2 of the next 10 patients in the Part 1 Expansion Cohort having cardiac toxicity would be. If the probability of cardiac toxicity were 2%, there would be 99.91% probability of 0 to 2 of 10 with toxicity; if it were 5%, there would be 98.8% probability; and if it were 10%, there would be 93% probability of 0 to 2 of 10 with toxicity. Thus, assuming the next 10 patients would have the same underlying per-patient probability of developing cardiac toxicity as the first 20 had, and it is likely to truly be at or below 10%, there is between a 93% and 99.9% probability that the next 10 patients enrolled in the Part I Expansion Cohort would have 0 – 2 toxicities and therefore 0 – 2 of 30 would have cardiac toxicity as per the original study design. Consequently, FDA approval was received on 12/14/15 to initiate enrollment in Part II of the study in parallel, while enrollment of the Part I Expansion Cohort is completed.

The fraction of subjects with immunogenicity, defined as a 3-fold increase in anti-HER2/neu antibody concentration (measured as mcg/mL) or a 4-fold increase in antibody dilution titers over baseline will be reported, along with 80% and 95% confidence intervals, at the following time points: Weeks 4 (after 1 vaccine dose), 8 (after 2 vaccine doses), 12 (after 3 vaccine doses), 28 (after 5 vaccine doses), 48 and 52 weeks and during extended follow-up for monitoring of cardiac adverse events at weeks 76, 100 and 124.

Finally, as a secondary objective, the fraction of subjects who have stable disease, an objective partial response or better by modified irRC will be determined along with appropriate confidence intervals with exceptions to the PR assessment at Week 12 as noted in Sections [3.5.1](#), [3.5.2](#) and [6.2.4](#). The fraction identified in this trial will potentially be useful information for design of any subsequent trials using this vaccine in both of the patient populations being studied.

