### **Quantitative Anti-HER2 Antibody Testing: Weeks 0, 8, 16, 24, 32, 40, 48, 60, 76, 100, and 124**

**Purpose:** To determine the immunogenicity of autologous Ad HER2 dendritic cell vaccination as measured by a 3-fold increase in anti-HER2/neu antibody concentration (measured as mcg/mL) or a 4-fold increase in antibody dilution titers over baseline.

**Specimen Processing:** 1 10mL Red Top Clot activator

Specimens will be processed by the Clinical Support Laboratory Leidos Biomedical Research, Inc. Serum will be aliquoted into vials and cryopreserved until ready for interrogation in batched specimen assays.

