### **Characterization of Vaccine-Induced Antibody Profiles Weeks 0, 8, 16, 24, 32, 40, 48, 60, 76, 100, and 124**

**Purpose:** To characterize vaccine-induced antibody profiles using HER2 peptide microarrays, examining reactivity to HER2 extracellular (EC), transmembrane (TM) and intracellular (IC) domains to document evidence of epitope spreading.

To characterize immunoglobulin sub-classes of anti-HER2 antibodies.

**Specimen Processing:** No additional specimens to be drawn.

Will utilize clinical specimens drawn and processed for quantitative anti-HER2 antibody testing.

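### Section 11.3 plans to report the primary immunogenicity fraction at Weeks 4, 12 and 28, when the current schedule takes no anti-HER2 serum, and leaves out Weeks 16, 24, 32 and 40, when it does

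*Combined protocol and SAP*

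**What the plan says.** Section 1.1.1 and the opening of Section 11 make immunogenicity a primary objective. It is the fraction of patients with a 3-fold rise in anti-HER2 antibody concentration, or a 4-fold rise in titer, over baseline. Section 11.3 says this fraction will be given with 80% and 95% confidence intervals at "Weeks 4 (after 1 vaccine dose), 8 (after 2 vaccine doses), 12 (after 3 vaccine doses), 28 (after 5 vaccine doses), 48 and 52", and again at Weeks 76, 100 and 124 of the extended follow-up.

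The sampling plan is in Appendix 6: "Quantitative Anti-HER2 Antibody Testing: Weeks 0, 8, 16, 24, 32, 40, 48, 60, 76, 100, and 124". The antibody profile has the same weeks, "Characterization of Vaccine-Induced Antibody Profiles Weeks 0, 8, 16, 24, 32, 40, 48, 60, 76, 100, and 124", and takes no blood of its own: "Will utilize clinical specimens drawn and processed for quantitative anti-HER2 antibody testing". The row "Anti-HER2 Ab/ Profile" in the Section 3.4 calendar carries the same schedule.

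Four further provisions bear on the point.
- Calendar footnotes 8-11 limit samples from Week 40 onward to patients who have not progressed. They also exclude research bloods from analysis once a patient starts a treatment that could affect the data.
- Footnote 17 creates a Week 52 visit only when a confirmatory scan is needed. Section 5.1 moves those evaluations to Week 60 for everyone else.
- Footnote 16 allows delays: "Dose can be delayed up to 8 weeks. The study will reset at the time of study resumption".
- Section 11.1 says that "vaccine safety, immunogenicity and preliminary activity will be determined for each dose level". Section 3.1.2 says that, if no DLT is seen, dose levels will be "assessed for the fraction of patients with immunogenicity and clinical outcomes to determine the biologically optimal vaccine dose".

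**The concern.** The analysis section names weeks for a primary endpoint that the sampling plan does not supply. Three of the four estimates that Section 11.3 labels by number of doses (after 1, 3 and 5) have no scheduled specimen at the stated week.

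The weeks that remain are not neutral. After Week 8, every listed week with a sample falls at Week 48 or later, and all of those come only from patients without progression. If response is related to remaining progression-free, those fractions describe a selected group. Samples without that restriction are scheduled at Weeks 16, 24 and 32, but the list does not name them. An analyst would have to depart from the list to use them, and would be choosing the readout weeks after the event, in an open-label study.

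**Working it through.** No sample size, power or alpha figure is involved, so the check compares two lists and then counts doses and intervals.

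**Inputs.** Reporting weeks are from Section 11.3. Sampling weeks are from Appendix 6. Vaccination at Weeks 0, 4, 8, 16 and 24 is from Section 3.1. The Week 40 restriction is from footnotes 8-11 of Section 3.4, and the Week 52/60 rule is from footnote 17 and Section 5.1.

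**Calendar check.** Matched to its 17 column headings, the antibody row is ticked at Weeks 0, 8, 16, 24, 32, 40, 48, 60, 76, 100 and 124. It is blank at Weeks 4, 12, 20, 28 and 36. This equals the Appendix 6 list exactly.

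**Side by side (post-baseline).**

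| Week | Listed in 11.3 | Anti-HER2 serum scheduled |
|---|---|---|
| 4 | yes | no |
| 8 | yes | yes |
| 12 | yes | no |
| 16 | no | yes |
| 24 | no | yes |
| 28 | yes | no |
| 32 | no | yes |
| 40 | no | yes, no progression only |
| 48 | yes | yes, no progression only |
| 52 | yes | only if a confirmatory scan is needed; no progression only |
| 60 | no | yes, no progression only |
| 76, 100, 124 | yes | yes, no progression only |

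**Counts.**
- Of 9 listed weeks, 5 have a routine sample (8, 48, 76, 100, 124), 3 have none (4, 12, 28) and 1 is conditional (52).
- Of 10 post-baseline sampling weeks, 5 are listed. Weeks 16, 24, 32 and 40 are not listed in any form. Week 60 enters only through its link to Week 52.
- From Week 8 to Week 48 no listed week has a sample: 48 − 8 = 40 weeks. This gap is in the list, not in the data.

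**Dose labels.** Doses given before each labelled week are: Week 4, {0} = 1; Week 8, {0, 4} = 2; Week 12, {0, 4, 8} = 3; Week 28, {0, 4, 8, 16, 24} = 5. The Week 8 count assumes that blood is drawn before that day's dose. The labels in Section 11.3 are therefore right, and the fault lies only in the sampling weeks. Of the four labelled points, only Week 8 is sampled.

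**Time since last dose.** Section 11.3 plans estimates 12 − 8 = 4 weeks after dose 3 and 28 − 24 = 4 weeks after dose 5. The first scheduled samples after those doses, if no dose is delayed and blood is drawn before that day's dose, are:
- after dose 3: Week 16, 16 − 8 = 8 weeks;
- after dose 5: Week 32, 32 − 24 = 8 weeks.

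If dose 4 is delayed by the full 8 weeks and the sample moves with the relabelled week, the Week 16 interval becomes 8 + 8 = 16 weeks. The Week 32 interval does not change this way, because no dose follows Week 24 in the five-dose schedule. No sample falls between dose 1 and dose 2 (Weeks 0 to 4), so an after-one-dose estimate is not available on the five-dose schedule.

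**The case against.** **The plan covers it already.** The opening of Section 11 ties the fraction to whatever time points are measured, which would take in Weeks 16, 24, 32 and 40. This stands in part: no data are lost, and reporting those weeks would not contradict the objective. It does not cure the conflict, because Section 11.3 then names its weeks one by one.

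**Other parts of the protocol show blood at Weeks 12 and 28.** The Correlatives row of Figure 11, as extracted, marks those weeks, though not Week 4. It names no assay, and the figure is visibly damaged: its vaccine row reads Weeks 0, 4, 8, 12, 16 and 20. The Week 12 and 28 draws in Appendix 9 are lavender-top tubes for NKT cells, not the red-top serum tube of Appendix 6. Neither outweighs the assay-specific schedule. The calendar is not spotless either. As extracted it ticks vaccine at Week 32, against five doses ending at Week 24, and those two places need reconciling. The plain text of Appendix 6 carries this point, and the calendar only supports it.

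**The dose choice is not shown to suffer.** A reader might infer that the mismatch undermines selection of the biologically optimal dose. The documents do not support that. Section 3.1.2 uses an immunogenicity fraction alongside clinical outcomes, names no week and does not refer to the Section 11.3 list. Sections 3.1 and 11.1 also warn that the mix of tumor types and HER2 levels may prevent such a dose from being identified. This objection stands.

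**Earlier patients may have been sampled differently.** The schedule examined is the version dated 07/22/2019. Section 11.3 reports that 20 patients had received at least two doses by 12/11/15. Whether any gave antibody serum at Weeks 4, 12 or 28 cannot be told from these documents. A reader might infer that no such samples exist, but that goes beyond the text. This objection also stands, and it shapes the fix.

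**Conclusion.** The inconsistency is real and should be corrected before analysis. Under the current version, 3 of the 9 reporting weeks for a primary endpoint have no scheduled specimen and 1 is conditional. Four sampled weeks are left out. Followed literally, the list gives one estimate before Week 48 (Week 8, after 2 of 5 doses) and otherwise only estimates in patients without progression, although unrestricted samples are scheduled at Weeks 16, 24 and 32.

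The consequence is limited. The endpoint is estimated with confidence intervals, and no sample size or stopping rule rests on it. It would be too strong to say that the primary immunogenicity objective cannot be met, because the samples needed to describe response after three or more doses are scheduled. An effect on the dose judgement is possible but not shown.

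The conclusion assumes that the Appendix 6 schedule is the operative one, and that same-day blood is drawn before the vaccine dose.

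**What to change.** Reconcile Section 11.3 with Appendix 6 and the calendar.

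1. Replace the reporting weeks with those sampled: 8, 16, 24, 32, 40, 48, 60, 76, 100 and 124. Keep the 80% and 95% intervals.
2. Count a Week 52 sample in place of Week 60 only where Section 5.1 makes the two alternatives, that is, for a patient whose evaluations were done at the confirmatory-scan visit. If a patient has both samples, use Week 60.
3. At each week give the denominator and the number of doses received. Patients may have delayed or stopped vaccination, so the week alone does not fix exposure.
4. State with the results that Week 40 and later include only patients without progression.
5. Before removing Weeks 4, 12 and 28, check whether patients treated under earlier protocol versions gave antibody serum then. If so, report those results as a supplementary set, marked as incomplete.

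This is a change of wording, with no added visit or blood draw. The price is that there is no routine estimate after one dose. The estimates after doses 3 and 5 come about 8 weeks or more after dosing instead of the planned 4, so a short-lived rise could be missed, and the report should say so. The change does not settle which week should inform the dose judgement in Section 3.1.2, which remains open in the plan.

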## **11.4 STUDY TERMINATION**

This study will be terminated for the following reasons:

- Completion of enrollment accrual and all scheduled monitoring studies for enrolled subjects.
- Development of clinically significant CTRCD toxicity (defined as a decrease in the LVEF of > 10 percentage points, to a value < 53%) in two or more of the first 10 patients enrolled in the study or four or more of the first 20 patients enrolled in the study.
- Failure to accrue study subjects in a timely manner.

## **12 HUMAN SUBJECTS PROTECTIONS**

### **12.1 RATIONALE FOR SUBJECT SELECTION**

Subjects targeted for enrollment in this study have tumors that express varying levels of HER2, a well-known oncogene that when present, is characterized by more aggressive disease in certain cancers e.g. breast cancer. Significant improvements in clinical outcomes have been realized through the HER2-directed therapies such as trastuzumab and lapatinib. However, despite these successes, the usefulness of these therapies is mitigated by the requirement for a specific level of HER2 expression i.e. HER2 3+ IHC and an equivocal or positive FISH result for trastuzumab to realize clinical outcomes, the continued need for drug administration, and the ultimate development of resistance to treatment with subsequent disease progression. All of these factors point to a need for more effective therapies targeting HER2 designed to address and overcome these issues.

Subjects from both gender groups and all racial/ethnic groups are eligible for this study if they meet the eligibility criteria. Pregnant women are excluded from participation in the trial because AdHER DC vaccine may have the potential for teratogenic or abortifacient effects.

### **12.2 PARTICIPATION OF CHILDREN**

Since this is the first in human clinical trial of this AdHER2 autologous dendritic cell vaccine and the potential safety risks are unknown, patients < 18 years of age will not be allowed to enroll in this study.

### 12.3 PARTICIPATION OF SUBJECTS UNABLE TO GIVE CONSENT

Adults unable to give consent are excluded from enrolling in the protocol. However, re-consent may be necessary and there is a possibility, though unlikely, that subjects could become decisionally impaired. For this reason and because there is a prospect of direct benefit from research participation (Section 12.5), all subjects  $\geq$  age 18 will be offered the opportunity to fill in their wishes for research and care, and assign a substitute decision maker on the “NIH Advance Directive for Health Care and Medical Research Participation” form so that another person can make decisions about their medical care in the event that they become incapacitated or cognitively impaired during the course of the study. Note: The PI or AI will contact the NIH Ability to Consent Assessment Team (ACAT) for evaluation as needed for the following: an independent assessment of whether an individual has the capacity to provide consent; assistance in identifying and assessing an appropriate surrogate when indicated; and/or an assessment of the capacity to appoint a surrogate. For those subjects that become incapacitated and do not have pre-determined substitute decision maker, the procedures described in MAS Policy 87-4 and NIH HRPP SOP 14E for appointing a surrogate decision maker for adult subjects who are (a) decisionally impaired, and (b) who do not have a legal guardian or durable power of attorney, will be followed.

### 12.4 EVALUATION OF BENEFITS AND RISKS/DISCOMFORTS

The AdHER2 DC vaccine being given in this study targets both the extracellular (EC) and transmembrane TM domains of the HER2 protein receptor. The goal of therapeutic vaccination with this product is to stimulate the patient’s own immune system to make *polyclonal antibodies* (and also potentially killer cells) that recognize HER2. It is hoped that that these antibodies will have a similar beneficial effect in controlling disease and potentially prolonging survival.

Use of trastuzumab in women with breast cancer has been shown to be associated with a small, but significant risk (about 7%) for developing cardiac dysfunction. It is usually observed in patients who have previously received chemotherapy that is known to affect the heart. The risk of cardiac dysfunction is greater (about 27%) when trastuzumab is given in combination with anthracycline chemotherapy drugs such as doxorubicin (Adriamycin) and cyclophosphamide (Cytoxan). Exactly how trastuzumab causes cardiac toxicity is unknown. It is also not known whether antibodies made by a person’s own immune system will cause cardiac dysfunction. Because of this, cardiac function will be monitored very closely while receiving the vaccine treatment and for 24 months following the last dose of vaccine. In addition, there are strict stopping rules included in this study for any signals of cardiac toxicity that would appear to be exceeding the 7% frequency observed with trastuzumab monotherapy. There are currently multiple clinical trials with vaccines using different platforms and approaches to target HER2 and to date there have been no reports of significant vaccine-associated cardiac toxicity.

The only other likely risk associated with receiving this vaccine is local injection site reactions i.e. discomfort, itching, redness, swelling, or soreness/pain at the site where the vaccine is injected into the skin. In addition, due to the proposed mechanism of action that includes a possible acute inflammatory response at focal sites of tumor, subjects may experience discomfort at sites of metastatic disease and/or acute reactive pleural or peritoneal effusions. There is a more remote potential for systemic symptoms such as fatigue, malaise or fever associated with vaccination but these are much less likely because patients are being given their own cells that have been transduced to express HER2. The AdHER2 vector used to transduce the patient’s

autologous dendritic cells is not replication competent and does not integrate into the human genome. The construct has specifically omitted the oncogenic intracellular domain of HER2 to ensure additional safety.

Unlike trastuzumab or pertuzumab that are monoclonal antibodies, we anticipate that therapeutic vaccination with the AdHER2 DC vaccine will induce a polyclonal antibody response that targets multiple epitopes of HER2, since the immunogen contains both the extracellular (EC) and transmembrane (TM) components of HER2. This could potentially be beneficial in patients who have failed trastuzumab, lapatinib or other HER2-directed therapies due to resistance since these agents only recognize one small component of the outer portion of HER2 and as a result, many tumors become resistant. Because we anticipate the development of polyclonal antibodies that recognize multiple sites in HER2, the vaccine may also be beneficial in patients with HER2+ solid tumors as well as adjuvant bladder cancer patients at high risk of disease recurrence for whom trastuzumab is not clinically approved or for those breast cancer who don't have sufficient expression of HER2 i.e. IHC <3+ or an equivocal or positive FISH result and hence weren't eligible for trastuzumab treatment, thereby addressing an unmet medical need.

Both of the currently available HER2 therapeutics, trastuzumab and lapatinib target the extracellular component of HER2. Trastuzumab's biologic activity is believed to work by binding to HER2 receptors and interfering with signaling controlling tumor growth and division, as well as signaling the immune system to destroy the cancer cells. Lapatinib is an orally administered tyrosine kinase inhibitor of both the HER2/neu protein and the epidermal growth factor receptor. A third agent currently being investigated in clinical trials is pertuzumab, which is also a humanized monoclonal antibody. It has a unique function in that it prevents HER2 receptor dimerization and subsequently blocks cell signaling. All of these agents must be administered exogenously and continuously for beneficial effect at great cost and often with significant discomfort to the patient.

All care will be taken to minimize side effects. Patients will be examined and evaluated prior to enrollment. All evaluations to monitor the treatment of patients will be recorded in the patient chart. If patients suffer any physical injury as a result of the participation in this study, immediate medical treatment is available at the NIH Clinical Center, Bethesda, Maryland.

Although no compensation is available, any injury will be evaluated and treated in keeping with the benefits or care to which patients are entitled under applicable regulations. In all publications and presentations resulting from this trial, patients' anonymity will be protected to the maximum extent possible. Authorized personnel from the National Cancer Institute (NCI) and Food and Drug Administration (FDA) or other regulatory authorities may have access to research files in order to verify that patients' rights have been safeguarded. In addition, patient names will be given to the Central Registration to register and verify patients' eligibility.

